6.2.4 Biomarkers (if applicable)

Unbiased screening approaches will be applied to plasma samples from patients in the two arms of the study. Protein profiling will be performed by the Keck MS & Proteomics Resources. microRNA screen will be conducted at the Yale Center for Genome Analysis. Prostaglandin measurements will be conducted by an external core facility with expertise in prostaglandin measurement (Vanderbilt Eicosanoid Laboratory). Proteomic, small molecule

(prostaglandin), or microRNA changes may be identified that represent novel biomarkers for labor.

Milk RNA extraction of de-identifiable milk samples will be performed at the [name] Lab at Cornell University. RNA sequence will be performed at the Genomic Core at Cornell University or sent to NovoGene for sequencing. Data analysis will be performed at the [name] Lab.

6.3 Study Procedures

Main Trial Study Procedures:

1. Recruitment

- A letter will be sent to all practicing obstetricians and midwives at each site to provide information about this study and to ask them if their patients may be approached for potential recruitment once they are admitted for labor induction.
- Trial information will be available on clinicaltrials.gov.
- All nulliparous women with singleton gestations at or greater than 36 weeks of gestation undergoing labor induction or augmentation are potentially eligible for screening.
- The research team at Yale may also utilize the Joint Data Analytics Team (JDAT) in two ways:
 - 1. Direct-to-patient recruitment method. This is a behind-the-scenes electronic medical record search run by JDAT for the Yale New Haven Health System (YNHHS), based on study-specific inclusion/exclusion criteria. This search will not identify potential participants to the researchers. Once JDAT identifies eligible patients, these potential participants will be sent a message via MyChart providing information about the research study and information on how to contact study personnel if they are interested in participating. Potential subjects who do not use MyChart may receive a paper mailing with the same information.
 - 2. We will request a report of patients who are potentially eligible and their treating obstetrician or midwife from JDAT through the Induction of Labor scheduling tool. We will request permission from the OB doctor/midwife to contact their patient directly to inform them of this research study. Given the number of potentially eligible patients and the time-sensitive nature of recruitment (must occur after induction is planned and before actual induction, which could be less than 1 and up to 7 days), it is not feasible to ask the treating provider to contact the patients first, and this would also place a significant burden on the treating provider. A member of the research team

will send the following message to the patient through MyChart or call the patient if MyChart is not available:

- Dear [Patient Name],

My name is [Name] and I am a [insert job title] at Yale University and part of the research team for the STIM Study. I spoke with your doctor/midwife, and we believe you may be eligible to participate in this free and confidential research study investigating two different methods of labor induction. One method involves nipple stimulation using a breast pump and the other uses intravenous oxytocin infusion according to standard of care and hospital protocol. If you enroll, you will also be asked to complete brief surveys at 5 different times. You will be compensated [\$X] each time you do a survey, for a total of [\$X]. If you're interested in learning more, please reply to this message or call [insert phone]. We will also be available to answer any questions while you are at Labor & Birth at Yale New Haven Hospital. If you choose not to participate, you will continue with your usual care from your doctor/midwife. Thank you for your time.

Sincerely,

[Name]

- Inclusion/exclusion criteria will be reviewed with the patient's chart and/or discussion with the patient's responsible physician or midwife prior to approaching the patient to ensure that she meets eligibility criteria.
- If a patient appears to meet criteria for the trial, she will be told about the study and asked for written informed consent to participate in the trial. Consent will be obtained from a trained research team member.

2. Baseline Procedures

In addition to information collected for eligibility, the following information will be obtained at randomization from a subject interview followed by a review of her chart:

- Indication for labor induction
- Demographic information
- Medical history
- Obstetrical history including outcome(s) of any prior pregnancies (e.g., ectopic pregnancy, spontaneous or elective abortion prior to 20 weeks of gestation)
- Social history
- Current pregnancy complications (e.g., hypertensive disorders of pregnancy, gestational diabetes, etc.)

- Estimated fetal weight based on ultrasound (if within 2 weeks of randomization) or Leopold maneuvers
- Group B Streptococcus carrier status

3. Study Interventions

Women randomized to nipple stimulation will undergo the following procedures (intervention arm):

- Nipple stimulation will be done in the hospital after subjects receive proper training, and under the direction of the study and nursing teams.
- Subjects will be encouraged to stimulate with the aid of an electric breast pump, but they will also have the option to perform nipple stimulation by hand if desired.
- Subjects will undergo a 5-minute tutorial on the use of the electronic breast pump and hand stimulation technique by the labor nurse or certified research staff. Information handouts will be given to the subject.

Women randomized to exogenous oxytocin infusion (control arm) will undergo the following procedures as current standard of care:

- Continuous fetal monitoring will be maintained as per hospital protocol.
- Oxytocin will be administered using only premixed oxytocin intravenous solutions prepared by the pharmacy **as per current standard of care.**
- Oxytocin will be initiated via infusion smart pump at a starting rate of 2 mU/min.
- Dosage may be increased every 15 minutes for 2-hours, then every 30 minutes thereafter.
- Rate changes for oxytocin administration are based on the assessment of all three of the following: fetal status, contraction status, and maternal coping
- Decreases of the infusion rate by 1 mU/min require reassessment after 15 minutes.
- Oxytocin maximum dosage should not exceed 20 mU/min per institutional policy.
- The oxytocin will be stopped, and the provider will be notified for the following reasons:
- If oxytocin has been discontinued, it may be restarted after a minimum of 15 minutes
 - If oxytocin had been discontinued for <40 minutes and the fetal heart rate tracing is reassuring and uterine activity has returned to normal, oxytocin may be restarted at no more than one half of the rate that resulted in the non-reassuring FHR and/or uterine tachysystole and then increased by 1 or 2 mU/min per original provider order

- If oxytocin had been discontinued for ≥ 40 minutes and the fetal heart rate tracing is reassuring and uterine activity has returned to normal, oxytocin may be restarted at 1 or 2 mU/min and increased by 1 or 2 mU/min per original provider order.
- The oxytocin line will be disconnected from the main IV line if it has been determined that a cesarean section will be performed.

4. Other Interventions

The use of amniotomy (if the subject has intact membranes) and other labor procedures will be at the discretion of each subject's responsible maternity care provider (pragmatic study) and considered standard of care. If standard of care is altered based on clinical decision making by the subject's responsible treating physician or midwife, the subject will still remain in the study as long as the subject does not withdraw her consent to continue in the study.

5. Subject Management and Follow-Up

All subjects will be monitored for progression of labor and their fetus' response to labor by their responsible treating obstetrician or midwife. Each subject will undergo individualized assessment by their treating obstetrician or midwife, and the clinical decision will be made by the treating obstetrician or midwife if or when subjects in the nipple stimulation arm will be switched to the standard of care with exogenous oxytocin administration. There can be no absolute cut-offs for time or contraction responses since standard of care dictates individualized assessments for labor progression and fetal response; each birth experience is unique. Subjects in both arms of the trial should be allowed adequate time to labor before considering the induction "failed" and proceeding to cesarean section. An induction will be considered "failed" after at least 24 hours of exogenous oxytocin administration has failed to generate regular (e.g., every 3 minutes) contractions and cervical change, as is considered standard of care (36). Additionally, exogenous oxytocin generally should be administered for at least 12 hours after membrane rupture before considering the induction to have failed as is considered standard of care. (37). The time devoted to cervical ripening and/or nipple stimulation will not be included when calculating the length of induction for diagnosing failed induction.

It is expected that the fetal heart rate and uterine activity will be monitored continuously during labor and that subjects will stay in the hospital until delivery once the induction is started as is considered standard of care. Aside from the interventions described above, labor and delivery management decisions will be left to the discretion of the subject's responsible maternity care provider as is considered standard of care.

Subjects will be administered study questionnaires at multiple timepoints, as outlined below. Questionnaires will be administered using the REDCap Survey tool, and electronic QR codes will be provided to the subjects via email or text message (whichever the subject prefers). Paper versions will also be available if requested.

After randomization, subjects will be asked to complete four questionnaires to establish baseline: the visual analog pain scale (28), the Edinburgh Postnatal Depression Scale (EPDS) (32), the Infant Feeding Intention Scale (IFI) (39), and the EQ-5D survey (41). Two hours after initiation of study intervention, subjects will again be asked to complete the visual analog pain scale (28) to assess their pain after intervention start.

During their hospital postpartum stay prior to discharge, subjects will be asked to complete three questionnaires: the visual analog pain scale (28) to rate their pain experienced during childbirth; the Labour Agency scale (29) to assess their feelings of control during childbirth; and the Birth Satisfaction Scale-Revised (BSS-R) (30) (31) to rate their satisfaction with the childbirth process. They will also be asked about whether they plan to attempt to breastfeed their infant. They will also be asked if they had any intrapartum expression of colostrum or breast milk, the quantity (mL or ounces) expressed if known, whether they collected and stored it for their baby, and whether they fed it to their baby.

After hospital discharge (preferably two weeks postpartum, but up to three weeks postpartum will be acceptable), all subjects, regardless of study group, will be asked to complete one questionnaire: the Perception of Milk Supply (40). The unique QR code or link to this electronic survey will be emailed or texted to the subject based on their preference. Follow-up phone call will be made if needed.

After hospital discharge (preferably six to eight weeks postpartum, but anytime within the window of four to twelve weeks postpartum will be acceptable), all subjects, regardless of study group, will be contacted to ask about any unanticipated outpatient or inpatient visits for them or their infants since discharge. Subjects will also be asked to complete two questionnaires: the Maternal Breastfeeding Evaluation Scale (33) and the EPDS (32).

After hospital discharge (6 months postpartum), all subjects will be asked to complete one questionnaire to assess infant feeding method.

Biospecimen Procedures:

Specimen collection will be conducted as described in the previously published methodology (38).

For patients in non-spontaneous labor, blood and urine will be collected at 1) prior to cervical ripening, 2) after cervical ripening, and 3) after 2 hours of treatment (IV oxytocin or nipple stimulation). This is a maximum of 3 blood samples per subject. For control patients in spontaneous labor, a blood and urine specimen will be obtained at enrollment. Blood may be drawn in several ways depending on what is clinically appropriate: (1) venipuncture; (2) IV catheter placed as part of standard of care (SOC); and/or (3) IV catheter placed for research purposes. The research IV may be placed in addition to the SOC IV and may be used instead of research venipuncture. That is, research venipuncture and research IV will not both occur at the same time (only one or the other).

Urine samples (amount variable by patient) will be collected mid-stream in a sterile screw-top container 1) prior to cervical ripening, 2) after cervical ripening, and 3) after 2 hours of treatment (IV oxytocin or nipple stimulation). If a patient has an indwelling foley catheter, urine from the tubing will be collected at the time of adequate contractions. If a patient is being intermittently catheterized for urine, a urine sample will be collected as able, but the patient will not undergo additional bladder catheterization for the purpose of this study.

Blood and urine samples may not be collected at one or more of the specified time points due to logistical issues (eg. patient enrolled after cervical ripening, labor floor acuity prevents nurse from drawing blood, patient delivers before time point, etc.) and/or clinical care taking precedence.

Proteomic profiling will be conducted by mass spectrometry at the Keck MS & Proteomics Resource. Prostaglandin measurements will be performed by an external core facility with expertise in prostaglandin mass spectrometry methods (Vanderbilt Eicosanoid Facility). microRNA profiling will be conducted via bulk RNA sequencing by the Yale Center for Genome Analysis/Keck Core.

Milk samples will be collected up to twice a day. Antepartum milk samples (10 drops to up to ½ teaspoon) will be collected from individuals in the nipple stimulation group during the intrapartum phase. Samples will be collected every 12 hours until labor. Volume will be determined by the mothers based on the amount of milk produced and how much they want to use to feed the infant postpartum.

Postpartum milk samples will be collected from IV oxytocin and nipple stimulation treatments participants at approximately 12, 24, and 48 hours postpartum. At 12, 24 and 72 hours 6-10 drops of milk (or more if participant allows) will be collected to a sterile tube using a pump or manually expressed from the breast. At ~48 hours postpartum, we will aim to collect 0.5-2.5ml of milk to perform all the sodium and milk conductivity assays mentioned below. If mothers are still hospitalized at 72 hours, additional samples will be collected every 12 hours up to twice per day (6-10 drops).

0.5ml of milk is needed for analysis of Sodium and milk conductivity, 0.5ml of milk for RNA analysis and 1ml of milk for macronutrients analysis.

Biological samples will be collected and stored at Yale and Weill Cornell Medicine (WCM) under secure, temperature-controlled conditions before shipment to [name] lab in Ithaca. At collection time, all samples will be de-identified and labeled with unique study ID numbers and time since delivery, which contain no personally identifiable information. Yale and WCM sites will use REDCap to code and manage the associated clinical data and sample collection records. A secure, access-restricted linkage key connecting study IDs to patient identifiers will be maintained solely by the local research teams. [name] lab will only receive de-identified samples and coded data labeled with the study ID, and will have no access to patient identifiers. Results generated by [name] lab will be uploaded to the WCM REDCap database using the matched study IDs provided with the samples, ensuring

all data remain de-identified and participant confidentiality is maintained throughout the study.

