Among the women enrolled in the translational sub-study at Yale, the following secondary outcomes will be explored:

- Plasma proteomic profiles (measured by mass spectrometry) after 2 hours of treatment comparing patients receiving IV oxytocin and nipple stimulation. Plasma samples from patients who have not undergone cervical ripening will be collected as additional control to account for differences achieved from cervical ripening alone. Plasma samples from patients in early spontaneous labor will be obtained to compare how closely nipple stimulation therapy and IV oxytocin approximate the molecular phenotype of spontaneous labor.
- Changes in plasma proteomic profiles from baseline (prior to treatment), 2 hours, and the time of adequate contractions in each treatment group
- Plasma micro-RNA profiles (measured by bulk RNA sequencing) after 2 hours of treatment among patients receiving IV oxytocin, nipple stimulation, and patients in early spontaneous labor.
- Changes in plasma micro-RNA profiles from baseline (prior to treatment), 2 hours, and the time of adequate contractions in each treatment group
- Urine prostaglandin profiles (measured by mass spectrometry) at 2 hours comparing patients receiving IV oxytocin, nipple stimulation, nipple stimulation who cross-over to IV oxytocin, un-ripened control patients, and patients in spontaneous labor.
- Changes in urine prostaglandin profiles from baseline (prior to treatment), 2 hours, and the time of adequate contractions in each treatment group

Among the women enrolled in the translational sub-study for milk collection, the following secondary outcomes will be explored:

- Changes in milk sodium and conductivity levels from before delivery (in the nipple stimulation therapy group only), and 12, 24, 48 hours after delivery. For mothers hospitalized for a longer period, additional samples at 72 hours will be collected or later up to twice a day.
- Milk macronutrient composition at 48 hours after delivery in each treatment group.
- Milk RNA profile at 48 hours after delivery in each treatment group.

The following secondary neonatal outcomes will be explored:

- Intrapartum fetal death or neonatal death (assessed until birth hospitalization discharge or death)
- Neonatal Apgar score ≤ 3 at 5 minutes of life
- Umbilical cord arterial pH < 7.0 or base excess > 12 mmol/L; or umbilical cord venous pH < 7.0 or base excess > 12 mmol/L if arterial blood sample not available

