2) The sample size of 988 for the primary outcome will be sufficient to detect a 9.4% or 10.8% absolute difference in breastfeeding as the sole source of nutrition (BSSN) at the time of delivery hospitalization postpartum discharge with 80% power and 90% power, respectively (two-sided test, $\alpha=0.05$). This represents the difference between an expected BSSN rate of 47% in the setting of synthetic oxytocin infusion without nipple stimulation (average rate at the study sites based on institutional data) and 56.4% (with 80% power) or 57.8% (with 90% power) with nipple stimulation therapy.

3) Assuming a 15% attrition rate at 2 weeks postpartum (the time frame for our primary cost-effectiveness analysis in Aim 3), the sample size of 988 will have 90% power for detecting a standardized effect size of 0.22 for the between-group difference in cost and difference in quality adjusted life years (QALY) (two-sided test, $\alpha=0.05$). This is considered a small effect size based on conventional criteria, hence if we observe an even larger effect size, we should be sufficiently powered.

The sample size for this biospecimen trial is based on the primary comparison, specifically the difference in primary biomarkers from baseline to after 2 hours of treatment between patients performing nipple stimulation therapy and those receiving IV oxytocin. Sample size calculations are based on differences between non-laboring and laboring patients from prior reports (Table). Sample size was determined to achieve 80% power to detect a difference with a two-tailed alpha level of 0.05. The final sample size of 48 per exposure group is based on the largest sample size required (IL1beta). Therefore, there is more than adequate power for the remainder of the biomarkers of interest.

To detect a 10 mM difference in sodium concentration between the intrapartum nipple stimulation therapy group and the immediate synthetic oxytocin infusion group at 48 hours postpartum, with a standard deviation of 20 mM, 80% power, and a significance level of 0.05, a sample size of 32 participants per group is required. Accounting for an expected 30% dropout rate, we plan to recruit 46 participants per group.

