The primary comparison for Aim 1 is the difference in biomarker concentration or MS counts from baseline to 2 hours of treatment between patients performing nipple stimulation therapy and those receiving IV oxytocin. Secondary comparisons evaluate the change with labor induction versus spontaneous labor. This unadjusted between-group comparison of the within-group change will be based on a Student's t-test, with a supportive analysis using Analysis of Covariance (ANCOVA) where the baseline biomarker level will be a covariate in a mean response profile model (MRP), which allows for different variances and covariances across time. The primary exposure variable will be treatment group with either compound symmetry (CS) covariance or heterogenous compound symmetry covariance (HCS) to account for the within-patient correlation in biomarker values across the time points of data collection; and the choice between the two covariance matrices will be made using a likelihood ratio test (LRT)

as these are nested models. Results will be summarized as estimated means of fold change at adequate contractions for each group and the between-group mean differences, with surrounding 95% Confidence Intervals. By specifying the model as an MRP, we can also conduct any comparisons of means (within/between groups across time), by using linear contrasts and the multivariate Wald Test. In the adjusted analyses, we will include in the MRP as covariates the between-group differences identified in the between-group comparisons. In a sensitivity analysis, since we will know the timing of each measurement relative to the initiation of treatment, we will use the actual time (compare linear, polynomial or spline effect of time) instead of the categorical time point in a linear mixed effects model (LME) with a random intercept for each woman and a possible random slope for each woman (also tested using an LRT). All biomarkers listed in the Table will be analyzed in the same manner, as all will be treated as continuous variables. For the exploratory hypothesis using the time to active labor, we will use a joint modeling approach: time to active labor modeled jointly with the mean trajectory of change over time in biomarker values; this model will allow us to estimate the between-group differences in the time to active labor, as it is also influenced by the biomarker values within each group.

Data Analysis Plan for the Milk Biospecimen Sub-Study:

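### On-treatment urine is collected at a time that depends on catheter status, which does not match the 2-hour prostaglandin outcome

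*Protocol*

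**What the plan says.** **Collection (Protocol 6.3, Biospecimen Procedures).** Blood and urine are taken before cervical ripening, after ripening, and "3) after 2 hours of treatment (IV oxytocin or nipple stimulation"). The paragraph on urine repeats these three times for mid-stream samples and then adds: "If a patient has an indwelling foley catheter, urine from the tubing will be collected at the time of adequate contractions". For women catheterized intermittently, "a urine sample will be collected as able", with no time given. The section accepts that some samples will be missed for logistical or clinical reasons.

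**Outcomes (Protocol 5.2.2).** The between-group outcome is "Urine prostaglandin profiles (measured by mass spectrometry) at 2 hours comparing patients receiving IV oxytocin, nipple stimulation" and further comparison groups. A second outcome is "Changes in urine prostaglandin profiles from baseline (prior to treatment), 2 hours, and the time of adequate contractions in each treatment group". The protocol thus counts 2 hours and adequate contractions as two different time points.

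**Analysis (Protocol 6.4.3.2).** The primary sub-study comparison is "the difference in biomarker concentration or MS counts from baseline to 2 hours of treatment", and every biomarker in the sample size table of 6.4.2, which includes PGE2 and PGF2a, is to be analyzed the same way. The same paragraph also states: "Results will be summarized as estimated means of fold change at adequate contractions for each group". A sensitivity model replaces the categorical time point with actual time since treatment start.

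**Sample size (Protocol 6.4.2).** The sub-study is sized on "the difference in primary biomarkers from baseline to after 2 hours of treatment". The table labels five markers as primary: oxytocin, IL1b, PAI-1, ICOS ligand and apolipoprotein A4. The prostaglandins are not among them.

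**The concern.** A between-group comparison at a fixed time needs all women sampled at that time, by a rule that does not depend on anything observed after randomization. Here the rule changes with the way urine is obtained. Catheter status at the on-treatment sample is a feature of the labor in progress, in an open-label trial that leaves labor procedures to the treating provider (Protocol 5.1 and 6.3). The time at which contractions become adequate is itself a response to treatment: the background (2.1) cites a small earlier trial in which breast stimulation shortened the time to contractions.

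At stake is the hypothesis in section 4.1 that urinary prostaglandin metabolites are higher with nipple stimulation. If samples from two time points are pooled as 2-hour values, a difference between arms could partly reflect when urine was taken. If they are not pooled, the 2-hour data may lack catheterized women, and the adequate-contractions data would consist only of them.

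**Working it through.** **Step 1. The collection rule set against the outcomes.**

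| How urine is obtained | On-treatment time in 6.3 | Usable at 2 hours | Usable at adequate contractions |
|---|---|---|---|
| Void | after 2 hours | yes | none scheduled |
| Indwelling catheter | at adequate contractions | depends on the reading (step 2) | yes |
| Intermittent catheterization | no fixed time | only if it happens to fall there | only if it happens to fall there |

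**Step 2. The possible readings of the catheter sentence.**

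- It replaces the 2-hour sample and is analyzed as the 2-hour value: the 2-hour comparison then mixes two sampling times.
- It replaces the 2-hour sample and is labelled adequate contractions: the 2-hour value is then missing for catheterized women.
- It is an extra sample: the 2-hour comparison is intact, but adequate-contractions urine is scheduled only for catheterized women, so the change outcome in 5.2.2 rests on that subset.

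Each reading leaves at least one urine outcome that the schedule does not serve.

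**Step 3. The plan's own scale.** Inputs from the table in 6.4.2: 48 per group, PGE2 SD 4.2, PGF2a SD 1, 80% power, two-sided 0.05.

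- Standard error = SD × √(2/48): 4.2 × 0.2041 = 0.86 for PGE2; 1 × 0.2041 = 0.20 for PGF2a.
- Detectable difference = (1.96 + 0.84) × SE = 2.40 ng/mL for PGE2 and 0.57 ng/mL for PGF2a (2.43 and 0.58 with the t distribution). The plan states 2.4 and 0.58, so both reproduce.

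**Step 4. Illustration for the first reading only.** Two inputs are assumptions, because the protocol gives neither: the gap in catheter use between arms, and the shift in level between the two sampling times. I take the shift as 25% to 50% of the tabulated group difference (10 ng/mL for PGE2, 3.7 ng/mL for PGF2a). Spurious difference = gap × shift, in either direction.

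- Gap of 20 points, PGE2: 0.20 × 2.5 = 0.5 to 0.20 × 5.0 = 1.0 ng/mL, which is 21% to 42% of 2.4.
- Gap of 20 points, PGF2a: 0.20 × 0.925 = 0.19 to 0.20 × 1.85 = 0.37 ng/mL, which is 32% to 64% of 0.58.
- Gaps from 0 to 30 points: 0 to 1.5 ng/mL for PGE2 and 0 to 0.56 ng/mL for PGF2a.

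With 40% and 60% catheterized, each arm's variance is SD² + shift² × 0.4 × 0.6. For PGE2 at the larger shift this is 17.64 + 25 × 0.24 = 23.64, so SE = √(2 × 23.64/48) = 0.99. The spurious difference is then 1.0/0.99 ≈ 1.0 SE, and a two-sided 5% test rejects about 17% of the time. Over the 25% to 50% range, the rate is about 9% to 17% for PGE2 and 13% to 27% for PGF2a.

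With equal use at 50% in both arms and the same shift in both, there is no bias. The SD still grows by √(1 + shift² × 0.25/SD²): at the 50% shift, √(1 + 25 × 0.25/17.64) = 1.16 for PGE2 and √(1 + 3.4225 × 0.25) = 1.36 for PGF2a.

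**Step 5. A caution on the PGF2a row.** A difference of 3.7 with SD 1 needs 2 per group (3 with the t distribution), but the table states 8. If 8 is right, the SD would be near 2.5, the SE 2.5 × 0.2041 = 0.51, and the 20-point illustration would fall from 0.9–1.8 SE (0.185/0.204 to 0.37/0.204) to 0.4–0.7 SE (0.185/0.51 to 0.37/0.51).

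**The case against.** The strongest reply is that the catheter sentence does not cancel the general rule. That rule covers all women not in spontaneous labor, the stated maximum of three applies to blood, and 5.2.2 wants urine at adequate contractions as well, so the sentence may describe an extra sample or be left over from another design. This stands as a possible reading, but then women who void have no such sample and the schedule still differs by catheter status.

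A reader might infer something stronger: that catheters are placed because of labor progress or analgesia, that adequate contractions are by definition later in labor than 2 hours, and that the 2-hour result is therefore biased by a calculable amount. The documents do not support this. They give no rate, reason or timing for catheter placement. The biospecimen text does not define adequate contractions, which could come before or after 2 hours. Nothing says that a catheter sample will be analyzed as a 2-hour value.

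Other limits also stand. The tabulated prostaglandin differences are a generous scale for two on-treatment samples, and the table does not say that they are urinary. Its SDs need not apply to change from baseline. The sample size statement concerns primary biomarkers and so supports the 2-hour time point for prostaglandins only weakly. The analysis section itself refers to adequate contractions.

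The actual-time model helps in part. However, it is only a sensitivity analysis, and it handles clock time, not contraction stage.

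**Conclusion.** The inconsistency is in the text and does not depend on any assumption: the collection rule varies with catheter status, while the between-group outcome is set at 2 hours and adequate contractions is a separate time point. The consequence is added variance, missing values, or bias of unknown direction and size. The figures in the illustration rest wholly on an assumed catheter gap and an assumed shift, and with equal use and equal shift the bias is zero. The reach is limited to urine prostaglandins, which are not labelled primary, in the Yale sub-study. The trial's primary outcome and all sample sizes are untouched. It should be corrected because a stated rule does not serve the stated outcome and the correction is cheap.

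**What to change.** - In 6.3, collect on-treatment urine 2 hours after treatment start however it is obtained, by void or from catheter tubing. Intermittent catheterization should still add no procedure for the study.
- If urine at adequate contractions is wanted for the change outcome in 5.2.2, schedule it for all women as able and label it as its own time point.
- In 6.4.3.2, reconcile the summary at adequate contractions with the 2-hour comparison.
- Record the actual time and method of each collection. Label catheter samples already taken at adequate contractions by that time point and do not analyze them as 2-hour values.

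The cost is a sentence in 6.3, a matching edit in 6.4.3.2 and the collection record. The 2-hour rule needs no extra procedure and no change in sample size; an adequate-contractions sample for all women, if wanted, would add a collection. The downside is small: some existing catheter samples leave the 2-hour comparison.
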